#### 6.3.2.7 Other secondary outcomes

Other secondary outcomes (mobility/ADLs) will also be summarised using proportions and analysed using appropriate regression models.

### **6.4 Sub-group Analyses**

These sub-group analyses will be conducted on the ITT. They will involve modelling the primary outcome as the independent variable and interaction of treatment and covariate of interest. Thus the modelling will be based on logistic regression and will be analysed in a similar way to the primary outcome (depending on whether clustering is present or not).

Sub-group effects will be tested through formal interaction tests (Brookes et al 2001). Power for sub-group effects is adequate to detect larger interactions provided variance in the sub-groups is reasonably similar (Brookes et al 2001). In addition to formal testing for treatment moderation using an interaction term we will make available either within the primary paper or elsewhere and without drawing inference, the effect sizes and 95% confidence intervals for the main outcomes for each pre-specified sub-group to ensure these data are available for future meta-analysists.

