### **2.7 Planned sample size**

The primary outcome is the fall related fracture rate, expressed as the fracture rate per person per unit time of observation over 18 months after randomisation of the General Practice.

In the UK, the annual fracture incidence per 100 men aged 55-74 years is 2.6 (95% CI 1.9 to 3.3); this rises to 7.6 fractures (95% CI 4.0 to 11.3) per 100 women aged of the same age range over 55 years (Donaldson et al, 2008).

Adjusting for differences in gender in the general population (ONS 2006) yields a fracture rate of 6 per 100 people (6%) aged over 70 years. This estimate does not account for repeat fractures within a person and hence is a conservative estimate of the fracture rate.

To have 80% power to detect, as significant ( $p < .05$ ), a 2% reduction in fracture rate, from 6% to 4% (relative risk reduction, 0.67), requires 1900 participants per arm, or 5,700 overall. Incorporating a design effect to adjust for varying degrees of modest clustering (ICC range .001 to .003), inflates the sample size estimate to 7800, or 2,600 per arm. Allowing for 10% loss to follow-up, yields a target sample size of 9,000 participants. To recruit 9,000 participants at 150 per practice requires 60 general practices.

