### **2.8 Planned subgroup analyses**

We have selected sub-group criteria using simple data available in primary care. We will run confirmatory sub-group analyses on fracture outcomes for the following:

- **Age:** We will examine whether interventions are best targeted to the oldest old ( $\leq 80$  years or  $\geq 81$  years).
- **Gender:** There is considerable excess risk of falling and fracture in women.
- **Previous history of falls in the last 12 months:** This is not well recorded in primary care, and hence will depend on self-report;
- **Frailty:** This will be based on the categorisation of the Strawbridge questionnaire - not frail (rarely or never/sometimes) versus frail (often/very often).

- **Cognitive impairment:** If there are sufficient numbers of people scoring less than 5 on the cognitive impairment sub-test, we will run a sub-group analysis with cut-points less than 5 or 5 or more.

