## **6. STATISTICAL ASPECTS**

The statistical analyses will be carried out using SAS (version 9.13).

All statistical tests will be two-sided and performed at the 5% significance level.

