##### *6.3.2.2 Primary outcome*

Fracture rate (per person per month) observation has a skewed distribution (heavy skewed in favour of zeros). We will explore the possible models that may account for this skew: (a) Poisson model; (b) zero inflated Poisson model; (c) negative binomial; (d) zero inflated negative model.

For the fracture rate (per person per month observation), we will assess this over the 18 months, using an 'offset' variable in the appropriate model, and also incorporate the general practice variable as the random effect.

Proportion of patients having at least one fracture, will be analysed using logistic regression models, with the random effect as general practice. The adjusted analysis will incorporate the appropriate covariates (as stated above).

Time to first fracture will be assessed using survival analysis methods.

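### Sub-group analyses pair the rate outcome with logistic regression, make the practice effect conditional on undefined clustering, and are called confirmatory without error control

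*SAP*

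**What the plan says.** Three parts of the SAP bear on this point.

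- **Outcome and model.** Section 6.4 describes "modelling the primary outcome as the independent variable and interaction of treatment and covariate of interest" and continues: "Thus the modelling will be based on logistic regression". Section 2.6 defines the primary outcome as a fracture rate per person-time over 18 months. Section 6.3.2.2 analyses that rate with a Poisson or negative binomial family model and an offset. Logistic regression appears in 6.3.2.2 for the proportion with at least one fracture, which 2.6 lists as secondary. Section 4.2, however, attaches the label of primary outcome to having at least one fracture, and says the sample size rests on that proportion.
- **Clustering.** Section 6.4 says the sub-group analysis will resemble that of the primary outcome "depending on whether clustering is present or not". For the rate, 6.3.2.2 will "also incorporate the general practice variable as the random effect", and it gives the logistic model a practice random effect as well. Neither is conditional.
- **Status and error rate.** Section 2.8 states: "We will run confirmatory sub-group analyses on fracture outcomes". It lists age, gender, falls history, frailty and, if numbers allow, cognitive impairment. Section 6 states: "All statistical tests will be two-sided and performed at the 5% significance level". No multiplicity rule for the sub-group tests appears.

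Section 6.4 also specifies formal interaction tests. It undertakes to publish effect sizes with 95% confidence intervals for each sub-group, as description only, for later meta-analyses.

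**The concern.** A logistic model of any fracture ignores repeat fractures and person-time, so it answers a different question from the primary rate analysis. Because 6.4 names the primary outcome, gives the model of a secondary one, and then refers back to the primary analysis, an analyst could defend either model after seeing the data.

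The clustering clause leaves a second choice open. General practice is the unit of randomisation, so variation between practices belongs in the standard error of any comparison between arms, whether or not it is visible in a particular sub-group. With no definition of when clustering counts as present, a real but small practice effect could be dropped. The sub-group intervals would then be too narrow, and later meta-analyses would give them too much weight.

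The confirmatory label invites readers to treat a significant interaction as established, although several interactions are each tested at 5%.

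**Working it through.** **The SAP's own figure.** Section 2.7 begins "To have 80% power to detect, as significant" and continues: "a 2% reduction in fracture rate, from 6% to 4% (relative risk reduction, 0.67), requires 1900 participants per arm, or 5,700 overall". With the two-sided pooled formula and no continuity correction:

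n = [1.96·√(2·0.05·0.95) + 0.842·√(0.06·0.94 + 0.04·0.96)]² / 0.02² = 1,863 per arm.

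This is within 2% of 1,900. The step to 2,600 per arm is a design effect of 2,600/1,900 = 1.368. At 150 per practice that implies an ICC of 0.368/149 = 0.0025, inside the stated range of 0.001 to 0.003. The clustering inputs are therefore consistent and can be reused.

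**Dropping practice: within-sub-group comparisons.** Inputs are 150 per practice and 10% loss (2.7), so 135 evaluable. A half-size sub-group, which is my assumption, has m = 67.5 per practice. Design effect DE = 1 + (m − 1)·ICC; SE understatement = 1 − 1/√DE; actual level of a nominal 5% test = 2·[1 − Φ(1.96/√DE)].

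| ICC | DE | SE understated by | Actual level |
|---|---|---|---|
| 0.001 | 1 + 66.5·0.001 = 1.0665 | 3.2% | 5.8% |
| 0.003 | 1 + 66.5·0.003 = 1.1995 | 8.7% | 7.4% |

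A beta-binomial simulation agrees. It used 20,000 runs, 20 practices per arm, 75 per practice in each sub-group level (no loss to follow-up), and event risks of 6% and 9%. The unadjusted within-sub-group test ran at 5.7% to 7.7%, against 5.9% to 7.6% from the formula with m = 75.

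**Dropping practice: the interaction test.** In the same simulation the unadjusted interaction test ran at 4.7% to 5.1%. Both levels of an individual-level factor share the same practice effect, which largely cancels in the difference.

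**Multiplicity.** Each test is at 5% and factors are taken as independent.

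- One test per factor: 1 − 0.95⁴ = 18.5% (four factors, cognition omitted) and 1 − 0.95⁵ = 22.6% (five).
- Two contrasts per factor sharing the advice arm (correlation 0.5): the chance of a false positive per factor is 0.0907, giving 1 − 0.9093⁴ = 31.6% and 1 − 0.9093⁵ = 37.9%.
- Five factors by two contrasts, all independent: 1 − 0.95¹⁰ = 40.1%.

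**Power, for context.** Suppose the full 6% to 4% effect occurs in one half and none in the other, with 2,600 per arm (1,300 per arm in each half) and no clustering. The log odds ratio is −0.427. Its interaction SE is √[3/(1,300·0.06·0.94) + 1/(1,300·0.04·0.96)] = 0.247. Power is Φ(0.427/0.247 − 1.96) = 41%.

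**The case against.** A reader might infer that the sub-group results would be wrong. The SAP does not support that. Inference in 6.4 rests on the interaction test, which keeps close to its nominal level when practice is ignored. The per-sub-group estimates are offered as description only. This stands, and confines the harm from the clustering clause to the intervals. It does not remove it, because those intervals are published for others to pool.

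Logistic regression is a valid analysis of any fracture, which is a listed outcome. It appears under the primary outcome heading in 6.3.2.2, section 4.2 labels any fracture as primary, and 2.8 speaks of fracture outcomes generally. At 6% against 4% the odds ratio is 0.653 and the risk ratio 0.667, so the scales differ little. This also stands: the defect is an unresolved choice of outcome and model. It is still a defect, since 6.4 names the primary outcome and both 2.6 and 6.3.2.2 make that a rate.

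Larger error rates can be derived from whole arms: at 150 per practice, dropping practice gives 6.7% to 10.3%. They do not apply here, because 6.3.2.2 keeps the random effect for those comparisons. The SAP also specifies no significance test for clustering, so how often practice would be dropped cannot be computed from it.

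On multiplicity, 6.4 does not say whether interactions are tested for each contrast, so the higher range is conditional. The 41% power does not contradict the SAP, which claims adequacy only for larger interactions.

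Two wording matters carry little weight. Calling the outcome the independent variable is a slip for dependent and cannot change a result. Naming only the interaction term is shorthand; nothing in the SAP excludes main effects, and 6.3.2.1 already includes age and gender.

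**Conclusion.** The point holds as a should-fix. Section 6.4 contradicts 2.6 and 6.3.2.2 on outcome and model, and makes the practice effect conditional on something it does not define. Section 2.8 claims a confirmatory status that the testing plan does not support.

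If practice is dropped, within-sub-group standard errors are understated by about 3% to 9%, and a nominal 5% comparison runs at about 5.8% to 7.4%. This assumes the SAP's ICC range applies within sub-groups, a 50/50 split spread evenly over practices, and 10% loss. The interaction test stays near 5%, provided both sub-group levels share the practice effect.

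The larger quantity is the chance of at least one false interaction: about 19% to 23% with one test per factor, and about 32% to 40% with both contrasts against advice, assuming independent factors. The primary analysis is untouched.

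**What to change.** In section 6.4:

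- Specify the primary rate model: fracture count as the dependent variable, log person-time offset, and terms for treatment, sub-group factor and treatment by factor. Report ratios of rate ratios with 95% confidence intervals.
- Keep the random-effects logistic model only for any fracture, named as a supporting outcome. Correct the primary-outcome label in 4.2 to match.
- Retain the practice random effect in every sub-group model, and delete the clause "depending on whether clustering is present or not".
- Change independent to dependent variable.

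In section 2.8, replace confirmatory by exploratory. If the confirmatory status is wanted, use one 2-degree-of-freedom treatment-by-factor test per factor across the three arms, with Holm adjustment over the factors tested.

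The cost is a change of SAP wording and slightly wider sub-group intervals. Holm adjustment, if chosen, would further reduce interaction power that is already modest.

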**Appendix 1. Searching for fracture events.**

The algorithm for ascertaining fractures has been presented in Bruce et al [2016].

HES APC database.

ICD-10 Diagnosis codes used to identify fracture events in Acute Patient Care (APC) dataset:

A fracture will be assigned if any one of the following occurs

- 1) A single code report (any one or more of the listed codes)
  - a) S02, , S12, S120, S121, S122, S127, S128, S129, S22, S220, S221, S222, S223, S224, S225, S228, S229, S32, S320, S321, S322, S323, S324, S325, S326, S327, S328, S42, S420, S421, S422, S423, S424, S427, S428, S429, S52, S520, S521, S522, S523, S524, S525, S526, S527, S528, S529, S62, S620, S621, S622, S623, S624, S625, S626, S627, S628, S72, S720, S721, S722, S723, S724, S727, S728, S729, S82, S820, S821, S822, S823, S824, S825, S826, S827, S828, S829, S92, S920, S921, S922, S923, S924, S925, S927, S929, T02, T08, T10, T12, T142, Z094, Z544.

Each reported code will be counted as one fracture. For all fractures, the data of admission will be used as the proxy for date of fracture.

- 2) A combined code report in the HES Acute Patient Care dataset (one of each list of codes i.e. 2(a) AND 2(b) has to be presented in the same episode record to define a fracture):
  - a) M80, M484, M485, M843
  - b) W00, W01, W02, W03, W04, W05, W06, W07, W08, W09, W10, W11, W12, W13, W14, W15, W16, W17, W18, W19, or R296

Each reported code pairing will be counted as one fracture. For all fractures, the data of admission will be used as the proxy for date of fracture.

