### ***Secondary outcomes***

Secondary outcomes will encompass the following:

- *Fracture rate per person month of observation for the entire available period of observation*

We have collected additional data on fractures from HES for a time period that extends beyond 18 months after randomisation. This data will also be summarised and analysed.

- Proportion of people sustaining one or more fracture over 18 months

- Time to first fracture

We will attempt to date all fractures. The date of fracture will be taken as the A&E attendance or HES episode admission date where these exist. In addition, we will check GP records for confirmation of fracture dates where these are recorded, with the exact date of fracture event if reported taking precedence over HES and A&E attendance if these differ.

- Fracture episodes

It is possible that people will experience multiple fractures from one fall. It will not be possible to consistently attribute fractures to a single fall event. Instead we will estimate fracture episodes. We will characterise all the fractures occurring on the same date as one episode. We will use statistical modelling to account for fractures occurring in the same individual and in the same episode. We will report and explore the number of episodes of fractures and recurrent fracture episodes. We may not be able to generate sufficient resolution in the data to assign fractures to episode. If so, we will not report these data (this will be apparent after the data cleaning is finalised).

- Fracture regions

We will estimate the difference in number of proximal femoral fractures (hip fractures) and fractures involving the distal radius (wrist fractures). Hip fractures were defined as verified fractures with a specific description of neck of femur or proximal femur. Fractures described as subtrochanteric, femoral shaft, distal femur, or simply femoral will not be categorised as hip fractures.

- Falls rate per person per month observation over the 18 months

- Proportion of people sustaining one or more fall over the 18 months
- mobility/ADLs:  
Questions on difficulties balancing on a level surface, ability to walk outside of the house, and average time spent walking.
- Frailty:  
A 16 item frailty questionnaire. We will report sub-domains and the overall domain scores for the follow up time points in which we have these data.
- Cognitive ability:  
A clock-drawing test used as for cognitive screening.
- Health related quality of life:  

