S521	Fracture of upper end of radius
S522	Fracture of shaft of ulna
S523	Fracture of shaft of radius
S524	Fracture of shafts of both ulna and radius
S525	Fracture of lower end of radius
S526	Fracture of lower end of ulna
S527	Multiple fractures of forearm
S528	Fracture of other parts of forearm
S620	Fracture of navicular [scaphoid] bone of wrist
S621	Fracture of other and unspecified carpal bone(s)
S622	Fracture of first metacarpal bone
	Fracture of other and unspecified metacarpal
S623	bone
S624	Multiple fractures of metacarpal bones
S625	Fracture of thumb
S626	Fracture of other and unspecified finger(s)
S627	Multiple fractures of fingers

S628	Fracture of other and unspecified parts of wrist and hand
S720	Fracture of head and neck of femur
S721	Pertrochanteric fracture
S722	Subtrochanteric fracture of femur
S723	Fracture of shaft of femur
S724	Fracture of lower end of femur
S727	Multiple fractures of femur
S728	Other fracture of femur
S729	Unspecified fracture of femur
S920	Fracture of calcaneus
S921	Fracture of talus
S922	Fracture of other and unspecified tarsal bone(s)
S923	Fracture of metatarsal bone(s)
S924	Fracture of great toe
S925	Fracture of lesser toe(s)
S927	Multiple fractures of foot
S929	Unspecified fracture of foot and toe
T142	Fracture of unspecified body region
Z094	Follow-up examination after treatment of fracture
Z544	Convalescence following treatment of fracture
M80	Osteoporosis with current pathological fracture
M484	Fatigue fracture of vertebra
M485	Collapsed vertebra, not elsewhere classified
M843	Stress fracture
W00	Fall due to ice and snow
W01	Fall on same level from slipping, tripping and stumbling
W02	Fall involving ice-skates, skis, roller-skates or skateboards
W03	Other fall on same level due to collision with another person
W04	Fall while being carried or supported by other persons

W05	Fall from non-moving wheelchair, nonmotorized scooter and motorized mobility scooter
W06	Fall from bed
W07	Fall from chair
W08	Fall from other furniture
W09	Fall on and from playground equipment
W10	Fall on and from stairs and steps
W11	Fall on and from ladder
W12	Fall on and from scaffolding
W13	Fall from, out of or through building or structure
W14	Fall from tree
W15	Fall from cliff
W16	Fall, jump or diving into water
W17	Other fall from one level to another
W18	Other slipping, tripping and stumbling and falls
W19	Unspecified fall
R296	Repeated falls

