### **List of HES A&E Codes**

In addition we will search for HES A&E codes as follows.

Code	Variable	HES Accident & Emergency
Diagnosis codes		
05	A&E Diagnosis code: 2 character	Dislocation/fracture/joint injury/amputation
052	A&E Diagnosis code: 3 character	Open fracture
053	A&E Diagnosis code: 3 character	Closed fracture
Treatment codes		
05	A&E Treatment code: 2 character	Plaster of Paris
33	A&E Treatment code: 2 character	Fracture review
101	A&E Treatment code: 3 character	Manipulation of upper limb fracture
102	A&E Treatment code: 3 character	Manipulation of lower limb fracture

All HES A&E codes will be presented for adjudication. Data from patient self-report forms and/or GP record will be used to confirm whether a fracture has occurred (for codes 05), and

for all other codes, we will review GP records and self-report data to ascertain type of fracture by the adjudication committee.

Search strategy for general practice.

A comprehensive search of the general practice patient records (READ Codes) has been undertaken for each practice to identify individuals with suspected fractures from the GP record. All GP records will presented to the adjudication committee to confirm a fracture and fracture details. All fractures will be given an ICD 10 code by the adjudication committee.

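### Appendix 1 lets aftercare codes and repeated inpatient codes count as new fractures, so the primary count can include duplicates and fractures from before randomisation

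*SAP*

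**What the plan says.** Appendix 1 gives two rules for finding fractures in the inpatient (HES APC) data. Under rule 1 the trigger is "A single code report (any one or more of the listed codes"; no second code or other source is needed. The list ends with "T142, Z094, Z544". The code table in the same appendix defines Z094 as "Follow-up examination after treatment of fracture" and Z544 as "Convalescence following treatment of fracture". The counting rule is "Each reported code will be counted as one fracture", and the admission date stands in for the fracture date. Rule 2 requires an M code and a fall code in the same episode record, and "Each reported code pairing will be counted as one fracture".

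Four other places bear on the count:

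- Section 2.6 makes a HES or GP report confirmatory without a self-report. It also states that two clinically qualified team members adjudicate fracture events.
- Section 2.5 promises that suspected events are validated blind to allocation.
- The Notes in Appendix 1 call for adjudication of the total when single-code and combined-code reports both occur. They also call for a breakdown where a code means several fractures without giving a number.
- For A&E data, every code goes to adjudication. Code 05 is checked for whether a fracture occurred, but "for all other codes, we will review GP records and self-report data to ascertain type of fracture".

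On dates, section 2.6 starts from the A&E or HES admission date and checks GP records, "with the exact date of fracture event if reported taking precedence over HES and A&E attendance if these differ". Section 2.7 sets the window at 18 months from randomisation of the practice.

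**The concern.** Neither Z094 nor Z544 denotes a new injury. Both record care after a fracture that has already been treated, yet each is enough to assign a fracture dated at the aftercare admission. The rule also has no step for the same injury code appearing again in a later episode or a readmission.

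This is the event definition of the primary outcome, so two kinds of error can enter the main analysis. A duplicate adds to the count of someone already counted, which raises the rate and adds within-person variation. An aftercare record for an injury before randomisation can create an event in someone with no fracture in the window. That second kind also affects the proportion with at least one fracture and the time to first fracture. Duplicates on later dates would in addition appear as recurrent episodes in the secondary outcome on fracture episodes, because that outcome merges only fractures with the same date.

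**Working it through.** **Following the rule through three cases.**

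1. A participant is admitted with S720 after randomisation and later has an admission coded Z544. Rule 1 gives two codes, so two fractures on two dates.
2. A participant has S720 in one episode and S720 again on readmission for the same injury. Rule 1 gives two fractures.
3. A participant breaks a bone before randomisation and has an admission coded Z094 afterwards. Rule 1 gives one fracture, dated inside the window.

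**Whether another provision removes these.**

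| Provision | Case 1 | Case 2 | Case 3 |
|---|---|---|---|
| Notes: adjudicate when single and combined codes coexist | not triggered | not triggered | not triggered |
| Notes: break down codes that mean several fractures | not triggered | not triggered | not triggered |
| 2.6: general adjudication; 2.5: blinded validation | no new-versus-repeat criterion stated | same | no check of the injury date against randomisation stated |
| 2.6: HES report confirmatory by itself | supports counting | supports counting | supports counting |
| 2.6: exact GP date overrides | changes a date, does not itself merge events | same | removes the event, but only if an exact date is recorded |

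**The plan's own figure.** Section 2.7 gives 1900 per arm for 6% versus 4%, 80% power and 5% two-sided. The pooled two-proportion formula gives 1863, within 3% of 1900. At 1900 per arm without clustering, power is 81%. The counting rule does not put that figure in doubt; it serves only as the base for the illustration below.

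**Illustration 1, false events (assumed).** Suppose both arms gain the same number of false events, a share f of the 6% control risk, all in people who would otherwise have none. The observed ratio is (0.04 + 0.06f) / (0.06 + 0.06f).

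| f (assumed) | Observed ratio | Power, 1900 per arm, no clustering |
|---|---|---|
| 0 | 0.040/0.060 = 0.667 | 81% |
| 10% | 0.046/0.066 = 0.697 | 77% |
| 20% | 0.052/0.072 = 0.722 | 73% |
| 30% | 0.058/0.078 = 0.744 | 69% |

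**Illustration 2, duplicates (assumed).** Suppose a share d of fractures is counted twice, equally in both arms. Both counts are multiplied by 1 + d, so the rate ratio does not move. Relative to counting each fracture once, the variance of the log rate is multiplied by (1 + 3d)/(1 + d)². A plain Poisson model takes that multiplier to be 1/(1 + d), so its standard error is too small by a factor of √[(1 + d)/(1 + 3d)]. The true type I error is 2[1 − Φ(1.96 √((1 + d)/(1 + 3d)))].

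| d (assumed) | Variance factor | Type I error, plain Poisson |
|---|---|---|
| 10% | 1.30/1.21 = 1.074 | 7.1% |
| 20% | 1.60/1.44 = 1.111 | 9.0% |
| 30% | 1.90/1.69 = 1.124 | 10.5% |

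Plain Poisson is one of four candidate models in section 6.3.2.2. The negative binomial, also listed there, allows for overdispersion.

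**The case against.** The best defence is that code counting is not the last step. Section 2.6 states adjudication without a trigger, section 2.5 adds blinded validation, and the Notes require a record of adjudications reviewed for consistency. Two clinicians looking at a Z544 record would probably see what it is. Where the GP record holds the exact injury date, a fracture from before randomisation falls outside the window. Appendix 1 also refers to a published algorithm that is not part of the SAP and may contain a de-duplication step. This stands to the extent that the SAP shows only that the count can include such events, not that it does. It does not remove the point: no stated criterion tells the adjudicators to drop aftercare or repeat records, and the written counting rule tells them the opposite.

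Some stronger readings are tempting but not supported:

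- **A&E code 33 (fracture review) is counted automatically.** It is not. It is absent from the inpatient lists, and all A&E codes are adjudicated. What remains is narrower: the stated purpose for that code is to find the type of fracture, not whether it is new.
- **Rule 2 counts one M code twice when a W code and R296 both accompany it.** The natural reading is that the condition is met once. A clarifying phrase is enough.
- **The dating rules contradict each other.** Appendix 1 calls the admission date a proxy and section 2.6 lets an exact GP date override it. This is a default with an override that lacks a cross-reference.
- **The result is biased towards one arm.** Duplicates in 20% of advice cases and 10% of intervention cases would give a spurious ratio of 1.10/1.20 = 0.92. Nothing in the SAP shows that inpatient aftercare coding differs by arm.
- **The duplicate variance factors lower the planned 80% power.** Section 4.2 says that the sample size rests on the proportion with at least one fracture, which a second count in the same person cannot change.

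**Conclusion.** The concern holds as a defect in a stated rule for the primary outcome. Rule 1 lets Z094 and Z544 assign a fracture by themselves and counts every reported code. The primary count can therefore include the same fracture more than once and can include fractures sustained before randomisation. The adjudication, validation and GP-date provisions reduce this in part, but none of them says that these records are removed.

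The SAP gives no frequency of aftercare or repeat coding, so the size is unknown. If the errors are equal across arms, false events pull the rate ratio towards 1 and duplicates add overdispersion. The tables show how far under assumed shares of 10% to 30%; they are not estimates for this trial, and they ignore clustering. No direction of bias between arms can be shown.

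**What to change.** Amend Appendix 1 as follows, before the count is finalised:

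1. Take Z094 and Z544 out of the codes that alone assign a fracture. Use them only as prompts for the existing blinded adjudication.
2. Send any repeat of the same code, or of a code for the same site, in a later inpatient episode to that adjudication. Count it only if a new injury is confirmed, including a separate fracture on the opposite side.
3. Count a fracture only if its adjudicated date is on or after practice randomisation.
4. Keep rule 2 events eligible, and count each M code once per episode however many fall codes accompany it.
5. State that adjudication of A&E fracture review also checks whether the fracture is new.
6. Cross-refer the admission-date proxy to the date precedence in section 2.6.

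The cost is a change of wording, a small de-duplication step within adjudication that is already planned, and a somewhat lower counted fracture rate.
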